6.1.3 Visit 4 (Day 84 \pm 6 Days)

All patients returning for Visit 4 (Day 84 ± 6 days) will undergo the following procedures:

- Recording of vital signs;
- Physical and neurological examination;
- Documentation of AEs and concomitant medications;
- Administration of the Columbia-Suicide Severity Rating Scale (C-SSRS);
- Administration of MMSE;
- Fasting (~10 hours) blood sampling for clinical chemistry and PD and PK parameters (see Section 7).
- Optional: performing of lumbar puncture for CSF sample (see Section 7);
- Study drug compliance check; and

Patients will receive a supply of study drug with instructions on how to take it. Patients will be given an appointment to return with all used and unused study drug at Day 126 (± 6 days).

6.1.4 Visit 5 (Day 126 ± 6 Days)

All patients returning for Visit 5 (Day 126 ± 6 days) will undergo the following procedures:

- Fasting (~10 hours) blood sampling for clinical chemistry and hematology;
- Recording of vital signs;
- Administration of the Columbia-Suicide Severity Rating Scale (C-SSRS);
- Documentation of AEs and concomitant medications;
- Study drug compliance check; and

Patients will receive a supply of study drug with instructions on how to take it. Patients will be given an appointment to return with all used and unused study drug at Day 168 (± 6 days).

6.1.5 End of Treatment Visit 6 (Day 168 \pm 6 Days)

All patients returning for Visit 6 (Day 168 \pm 6 days) will undergo the following procedures:

- Recording of weight;
- Recording of vital signs;
- Performing 12-lead ECG;
- Fasting (~10 hours) blood sampling for hematology, clinical chemistry, and PD and PK parameters (see Sections 7 and 8.7);
- Collection of urine sample for urinalysis;
- Physical and neurological examination;
- Documentation of AEs and concomitant medication;
- Administration of the Columbia-Suicide Severity Rating Scale (C-SSRS);
- Administration of MMSE and CFC;
- Performing of lumbar puncture for CSF sample; and
- Study drug compliance check

6.1.6 End of Study Visit 7 (Day 198 \pm 6 Days)

Patients will be contacted by phone for a safety follow-up (Visit 7) approximately 4 weeks (±6 days) after the End of the Treatment Visit (Visit 6) for collection of AEs.

Early Termination Visit and Withdrawal Procedures

The end of the study for patients completing the study is Visit 7. For patients who are withdrawn from the study prior to completion, all procedures planned to be performed at the End of Treatment (EOT) Visit (Visit 6) will be conducted at an Early Termination Visit if possible.

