3.1.3 Safety Follow-up Period

Patients will be contacted by phone for a Safety Follow-up Visit (Visit 7) approximately 4 weeks (+/- 6 days) after the end of the Treatment Period for collection of adverse events (AEs).

Study Indication

The indication for this study is early AD.

Coronavirus Disease 2019 Contingency Measures

In cases of coronavirus disease 2019 (COVID-19) limitations, it is the Investigator's responsibility to assure the safety of patients, including phone or video contact to assess the patient's well-being including any AE, collection of study samples, and clinical data as best as possible, and direct shipment of study drug to the patient, if necessary. Where available and appropriate, home health care may be considered to facilitate monitoring of safety and study continuity. Documentation of these cases and the study site's management of patients should be recorded in the Investigator

study files. In the absence of a COVID-19 impact, it is expected that Investigators and patients follow the protocol requirements as set forth.

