8 SAFETY ASSESSMENTS

Adverse Events

An AE is defined as any untoward medical occurrence in a clinical investigation patient administered a pharmaceutical product, which does not necessarily have a causal relationship with this treatment. An AE can therefore be any unfavorable and/or unintended sign (including an abnormal laboratory finding), symptom, or disease temporally associated with the use of an investigational medicinal product, whether or not related to the investigational medicinal product. All AEs, including observed or volunteered problems, complaints, or symptoms, are to be recorded on the appropriate eCRF.

AEs, which include clinical laboratory test variables, will be monitored and documented from the time of first dose of study drug until the end of the study. Patients or their study partner should be instructed to report any AE that they experience to the Investigator, whether or not they think the event is due to study drug. Beginning at the date of the first dose of study drug, Investigators should make an assessment for AEs at each visit and record the event on the appropriate AE eCRF.

Wherever possible, a specific disease or syndrome rather than individual associated signs and symptoms should be identified by the Investigator and recorded on the eCRF. However, if an observed or reported sign or symptom is not considered a component of a specific disease or syndrome by the Investigator, it should be recorded as a separate AE on the eCRF. Additionally, the condition that led to a medical or surgical procedure (eg, surgery, endoscopy, tooth extraction, or transfusion) should be recorded as an AE, not the procedure itself.

Any medical condition already present at the date of the first dose of study drug should be recorded as medical history and not be reported as an AE unless the medical condition or signs or symptoms present at baseline change in severity, frequency, or seriousness at any time during the study. In this case, it should be reported as an AE.

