All SAEs occurring from the time of the first dose of study drug until 30 days following the last administration of study drug must be reported to within 24 hours of the knowledge of the occurrence. After the 30-day reporting window, any SAE that the Investigator

considers related to study drug must be reported to Sponsor/designee.
To report the SAE, complete the paper SAE report form and forward the form by fax or email to at a graph or call the sAE reporting line (phone number listed below), within 24 hours of awareness. Simultaneously, the investigator must record the SAE and any additional information on the relevant source documentation/eCRF, as appropriate.
The Sponsor/designee or Investigator will report the SAEs through the web portal ToetsingOnline to the accredited IEC that approved the protocol, within 7 days of first knowledge for SAEs that result in death or are life threatening followed by a period of maximum of 8 days to complete the initial preliminary report. All other SAEs will be reported within a period of maximum 15 days after the Sponsor/designee or Investigator has first knowledge of the serious adverse events.
Safety Contact Information: SAE reporting line – Europe: Telephone: Fax: Email:
Follow-up Reports
The Investigator must continue to follow the patient until the SAE has subsided or until the condition becomes chronic in nature, stabilizes (in the case of persistent impairment), or the patient dies.
Within 24 hours of receipt of follow-up information, the Investigator must update the paper SAE form and submit any supporting documentation (eg, patient discharge summary or autopsy reports) to via fax or email. Simultaneously, the investigator must record the updates and any additional information on the relevant source documentation/eCRF, as appropriate.
Pregnancy Reporting
If a patient becomes pregnant during the study or within the safety follow-up period defined in the protocol, the Investigator is to stop dosing with study drug immediately and the patient should be withdrawn from the study. Early termination procedures should be implemented at that time.
A pregnancy is not considered to be an AE or SAE; however, it must be reported to within 24 hours of knowledge of the event. provide the Investigator/site the Exposure In Utero (EIU) form for completion. The Investigator/site must complete the EIU form and fax/email it back to

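### The Visit 7 safety call can fall before the protocol's own 30-day SAE window closes, its timing is stated inconsistently, and whether it applies to withdrawn patients is left open

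*Protocol*

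**What the plan says.** **SAE window.** Protocol Section 8, SAE reporting procedures, covers "All SAEs occurring from the time of the first dose of study drug until 30 days following the last administration of study drug". Later SAEs remain reportable if the investigator considers them drug-related.

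**AE window.** Section 8, Adverse Events, says AEs "will be monitored and documented from the time of first dose of study drug until the end of the study".

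**Visit 7.** Section 6.1.6 sets the call "approximately 4 weeks (±6 days) after the End of the Treatment Visit (Visit 6) for collection of AEs". Section 3.1.3 uses the same interval but counts from the end of the Treatment Period. The heading of 6.1.6 and the Appendix A schedule give Day 198 ±6. SAP Section 2.2.1 repeats both the 4-week interval (in its text) and Day 198 (in Table 1).

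**End of study for a patient.** "The end of the study for patients completing the study is Visit 7".

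**Withdrawn patients.** The Early Termination paragraph in Section 6 says "all procedures planned to be performed at the End of Treatment (EOT) Visit (Visit 6) will be conducted at an Early Termination Visit if possible". Section 4, Withdrawal Criteria, asks staff to make every effort to complete those assessments and lets the patient decline the full panel. Neither place mentions Visit 7. Appendix A puts early termination in the Visit 6 column, followed by the follow-up column, and no footnote says whether that column applies after early termination.

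**The concern.** The safety endpoint is the incidence of AEs and SAEs. A site can follow the stated visit windows exactly and still make its last enquiry before the protocol's own SAE window has closed. After that call a completer's study is over and no further contact is scheduled. An event in the remaining days is then known only if the patient or study partner volunteers it, and these patients have early Alzheimer's disease.

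The position of withdrawn patients is less clear still. Reasons for withdrawal include SAEs and clinically significant AEs, and withdrawn patients are not replaced. The Visit 6 procedures to be done at early termination include a lumbar puncture, and no contact after it is expressly required. The pregnancy reporting rule also depends on a protocol-defined safety follow-up period, which is unclear for these patients.

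With 10 to 15 patients, each SAE carries visible weight in the reported incidence.

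**Working it through.** **Inputs.** Last planned dose Day 168 (Section 5.1.3). Visit 6 on Day 168 ±6, that is Days 162 to 174 (Section 6.1.5). SAE window 30 days after last dose (Section 8). Visit 7 at 4 weeks ±6 days (3.1.3, 6.1.6) or Day 198 ±6 (heading of 6.1.6, Appendix A).

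**1. The plan's own figures.** The stated duration of about 36 weeks reproduces with the longest screening period: 8 + 24 + 4 = 36. The stated Visit 7 day does not follow from the stated interval: 168 + 28 = 196, whereas Day 198 is 168 + 30.

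**2. Reference case: last dose and Visit 6 both on Day 168.** The SAE window closes on Day 168 + 30 = 198. A call before Day 198 is counted as early.

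| Visit 7 rule | Permitted days | Days after last dose | Early days | Largest shortfall | Shortfall on target |
|---|---|---|---|---|---|
| 4 weeks ±6 | 190–202 | 22–34 | 190–197: 8 of 13 | 30 − 22 = 8 days | 30 − 28 = 2 days |
| Day 198 ±6 | 192–204 | 24–36 | 192–197: 6 of 13 | 30 − 24 = 6 days | 0 days |

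These are two separate windows; neither rule alone gives 22 to 36 days.

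**3. Letting Visit 6 move over Days 162 to 174.** The documents do not fix the last-dose day when Visit 6 is not on Day 168, so three assumptions are shown. The 4-week rule is counted from Visit 6, as in 6.1.6. Entries are days from last dose to call.

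| Assumed last dose | 4 weeks ±6 after Visit 6 | Day 198 ±6 |
|---|---|---|
| Day of Visit 6 | 22–34 | 18–42 |
| Earlier of Visit 6 and Day 168 | 22–40 | 24–42 |
| Always Day 168 | 16–40 | 24–36 |

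For example, the 16 is 162 + 22 − 168, and the 18 is 192 − 174. Every reading allows a call before day 30, and every reading also allows one after it.

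**4. Withdrawn patients.** No arithmetic applies. The Visit 7 text speaks of patients in general and the schedule places follow-up after the shared end-of-treatment and early-termination column, which points towards a call. Section 6.1.6 anchors the call to Visit 6, and the sentence that ends a patient's study at Visit 7 is confined to completers, which points away from one. The end-of-study definition in Section 10 concerns the last patient in the trial, so it does not settle when a withdrawn patient's AE collection stops.

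**5. Weight of one event.** One patient is 1/15 = 6.7% to 1/10 = 10% of the sample.

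**The case against.** The strongest reply is that the protocol does not leave the 30 days uncovered. The SAE reporting duty stands whatever the date of the call and makes no exception for withdrawn patients. Patients and study partners are told to report any AE, and patients carry a card with contact details for an SAE. A reader might infer that an early call amounts to a lapse in SAE coverage. The documents do not support that: what may lapse is active questioning.

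A reader might also infer that withdrawn patients have no contact after treatment, or that someone withdrawn for an SAE is followed least. Neither is supported:

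- The Early Termination Visit is planned, and staff must make every effort to complete its assessments. What a patient may decline is the full panel, which is not the same as refusing the visit or a question about AEs.
- At least 3 contact attempts are required for patients lost to follow-up.
- The Visit 7 wording does not exclude withdrawn patients.
- An SAE already reported is followed until it subsides, becomes chronic or stabilises, or the patient dies, and clinically significant laboratory values have a similar rule. This protects follow-up of known events, though it does not look for new ones.

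On timing, the interval is described as approximate, and Day 198, the only study day given, coincides with the end of the SAE window. A call on that day loses nothing if the last dose was on Day 168. This is a fair reply to the 2-day difference on target. It does not deal with the early part of either window.

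Finally, 8 of 13 and 6 of 13 count calendar days. They are not probabilities of an early call, still less of a missed SAE. The 6.7 to 10 percentage points are what any single event is worth at this sample size, not an estimate of bias.

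**Conclusion.** The point holds as a gap in active ascertainment and an inconsistency in the text. Visit 7 need not reach the end of the protocol's SAE window. In the reference case it can fall up to 8 days short under the 4-week rule and up to 6 days short under the Day 198 rule. Those figures assume that last dose and Visit 6 both fall on Day 168; the Visit 6 window widens the ranges as shown, by an amount that depends on the actual last-dose day.

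For withdrawn patients, the supportable statement is that the text neither requires nor rules out a call after early termination and does not say when their AE collection ends.

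How many events would be missed cannot be worked out from the documents. The matter deserves correction because following the windows as written can close active enquiry too soon for the protocol's own rule, and the remedy is cheap.

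**What to change.** Reconcile Protocol Sections 3.1.3 and 6.1.6, the AE and SAE periods in Section 8, Appendix A, and SAP Section 2.2.1, so that they state:

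- one timing for the safety call, counted from the date of last dose and no earlier than the end of the SAE window the protocol already sets;
- that the call applies to every patient who took at least one dose, whether completed or withdrawn;
- that AE collection ends at that call for both groups, leaving the existing rules for following known SAEs and for reporting later related SAEs as they are.

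The cost is wording, a few calls moved later by some days, and one call per withdrawn patient.

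If follow-up is already complete, list in the CSR each patient's interval from last dose to last safety contact and identify those below 30 days, so that readers can see how much of the window was actively covered.

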7 PHARMACODYNAMIC AND PHARMACOKINETIC ASSESSMENTS

Blood samples for lipoproteins and apolipoproteins must be obtained under fasting conditions (ie, after the patient has fasted for ~ 10 hours). For the purposes of this study, fasting will be defined as nothing by mouth except water and any essential medications. If a patient is not fasted, the Investigator will reschedule the visit as soon as possible.

Primary Pharmacodynamic Endpoint

The primary PD endpoint is the change from baseline in levels of ApoA-I, ApoE, small HDL particles, in both CSF as well as plasma and ABCA1-driven cholesterol efflux in CSF measured at Day 168.

Exploratory Pharmacodynamic Endpoints

Exploratory analyses may be performed to further investigate the PD of obicetrapib. These may include, but might not be limited to, the following assays at selected time points:

Changes From Baseline Levels in Lipoproteins and Apolipoproteins in Plasma

At Baseline (Visit 2), at Day 84 (Visit 4), and the End of Treatment (Day 168, Visit 6), the following parameters will be measured:

- LDL-C
- Total cholesterol (TC)
- Non-HDL-C
- TG
- ApoB

Changes From Baseline Levels in Lipoproteins and Apolipoproteins in CSF and Plasma

At Screening (Visit 1) or Baseline (Visit 2), at Day 84 (Visit 4), and at the End of Treatment (Day 168, Visit 6), the following parameters will be measured:

- HDL-C
- HDL-ApoE
- Apolipoprotein A-II (ApoA-II)

Note, baseline levels of CSF lipoproteins and apolipoproteins will be determined at Screening (Visit 1) since CSF sampling is required for inclusion. Baseline levels of plasma lipoproteins and apolipoproteins will be determined at Baseline (Visit 2). CSF sampling for CSF lipoproteins and apolipoproteins at Day 84 (Visit 4) is optional.

Change From Baseline Levels in AD Biomarkers in CSF

At Screening (Visit 1), at Day 84 (Visit 4), and at the End of Treatment (Day 168, Visit 6), the following parameters will be measured in the CSF:

- Tau and phosphorylated tau at Thr181 (p-Tau 181)
- $A\beta_{1-42}$, $A\beta_{1-40}$, $A\beta_{1-42}/A\beta_{1-40}$ ratio
- Neurogranin
- Neurofilament light
- Glial fibrillary acidic protein (GFAP)
- sTREM2
- YKL40

- Inflammatory markers (eg, interferon [IFN]-γ, IL-10, IL-12p70, IL-17A, IL-6, TNF-α)

Note, CSF sampling for AD biomarkers in CSF at Day 84 (Visit 4) is optional.

Change From Baseline Levels in AD Biomarkers in Plasma

At Baseline (Visit 2), at Day 84 (Visit 4), and the End of Treatment (Day 168, Visit 6), the following parameters will be measured in the plasma:

- Tau and p-Tau epitopes
- $A\beta_{1-42}$, $A\beta_{1-40}$, $A\beta_{1-42}/A\beta_{1-40}$ ratio
- Neurofilament light

Correlation Between the Change From Baseline Levels in CSF p-Tau 181 and CSF ApoA-I, ApoE, and Cholesterol Efflux Capacity

At Screening (Visit 1) and at the End of Treatment (Day 168, Visit 6), p-Tau 181, ApoA-I, ApoE, and cholesterol efflux capacity will be measured in the CSF.

Change From Baseline Levels in 24-Hydroxycholesterol and 27-Hydroxycholesterol in CSF and Plasma

At Baseline (Visit 2), Day 84 (Visit 4), and the End of Treatment (Day 168, Visit 6), 24-hydroxycholesterol and 27-hydroxycholesterol will be measured in the CSF and plasma samples.

Note, CSF sampling for 24-hydroxycholesterol and 27-hydroxycholesterol in CSF at Day 84 (Visit 4) is optional.

Exploratory Cognition Endpoints

Disease Progression Measured With the Cognitive-Functional Composite

At Baseline (Visit 2) and the End of Treatment (Day 168, Visit 6), the CFC test will be administered to allow tracking of disease progression.

The CFC test was designed to improve the measurement of progression in early dementia stages of AD by providing a short and clinically relevant measure focusing on the cognitive domains and activities of daily living that are sensitive to decline in early AD.

The CFC combines the Short Version of the Amsterdam Instrumental Activities of Daily Living Questionnaire (A-IADL-Q-SV) and a brief neuropsychological test battery focusing on episodic memory and executive functions^{29,30}. The psychometric quality of the CFC was evaluated in the Catch-Cog study; an international, multi-center, independent longitudinal validation study including individuals with MCI and mild dementia due to AD²⁹. The CFC was found to have good test-rest reliability, and patients and caregivers experienced the content of the CFC as relevant and the administration as user-friendly^{30,31}. Further, it was shown that the CFC has good construct validity and quality for the target population, as evidenced by associations with clinical and biological measures of disease severity^{32,33}, and limited range restrictions in scoring at baseline³³.

The cognitive component includes seven existing cognitive tests that are administered by a trained rater (duration: 20-25 minutes). The A-IADL-Q-SV measures 30 cognitively complex instrumental activities of daily living, and is completed independently by the study partner on a tablet computer (duration: 10-15 minutes). The seven existing cognitive tests include the Alzheimer's Disease Assessment Scale-Cognitive (ADAS-Cog) Word Recognition, the

ADAS-Cog Orientation, the ADAS-Cog Word Recall, the Digit Span Backward Task, the Controlled Oral Word Association Test, the Category Fluency Test, and the Digit Symbol Substitution Test.

Mini-Mental State Examination

At Screening (Visit 1), Baseline (Visit 2), Day 84 (Visit 4), and the End of Treatment (Day 168, Visit 6), the MMSE will be administered.

The MMSE is a cognitive screening test originally designed for the grading of dementia severity. The MMSE test can be performed in approximately 5 to 10 minutes. The MMSE assesses different aspects of cognition: orientation, registration, attention and calculation, recall, language, repetition, and complex commands.

MMSE scores range from 0 to 30, with a score of 24 or higher indicating normal cognition.

Exploratory Pharmacokinetic Endpoint

Mean Plasma Levels of Obicetrapib at Steady State in CSF and Plasma

At Screening obicetrapib concentrations will be measured in the CSF. At Day 1 (Visit 2) obicetrapib concentrations will be measured in plasma. At Day 84 (Visit 4) and the End of Treatment (Day 168, Visit 6), obicetrapib concentrations will be measured in the CSF and plasma samples.

8 SAFETY ASSESSMENTS

Adverse Events

An AE is defined as any untoward medical occurrence in a clinical investigation patient administered a pharmaceutical product, which does not necessarily have a causal relationship with this treatment. An AE can therefore be any unfavorable and/or unintended sign (including an abnormal laboratory finding), symptom, or disease temporally associated with the use of an investigational medicinal product, whether or not related to the investigational medicinal product. All AEs, including observed or volunteered problems, complaints, or symptoms, are to be recorded on the appropriate eCRF.

AEs, which include clinical laboratory test variables, will be monitored and documented from the time of first dose of study drug until the end of the study. Patients or their study partner should be instructed to report any AE that they experience to the Investigator, whether or not they think the event is due to study drug. Beginning at the date of the first dose of study drug, Investigators should make an assessment for AEs at each visit and record the event on the appropriate AE eCRF.

Wherever possible, a specific disease or syndrome rather than individual associated signs and symptoms should be identified by the Investigator and recorded on the eCRF. However, if an observed or reported sign or symptom is not considered a component of a specific disease or syndrome by the Investigator, it should be recorded as a separate AE on the eCRF. Additionally, the condition that led to a medical or surgical procedure (eg, surgery, endoscopy, tooth extraction, or transfusion) should be recorded as an AE, not the procedure itself.

Any medical condition already present at the date of the first dose of study drug should be recorded as medical history and not be reported as an AE unless the medical condition or signs or symptoms present at baseline change in severity, frequency, or seriousness at any time during the study. In this case, it should be reported as an AE.

Clinically significant abnormal laboratory or other examination findings that are detected during the study or are present at the date of the first dose of study drug and significantly worsen during the study should be reported as AEs, as described below. The Investigator will exercise his or her medical and scientific judgment in deciding whether an abnormal laboratory finding or other abnormal assessment is clinically significant. Clinically significant abnormal laboratory values occurring during the clinical study will be followed until repeat tests return to normal, stabilize, or are no longer clinically significant. Abnormal test results that are determined to be an error should not be reported as an AE. Laboratory abnormalities or other abnormal clinical findings should be reported as an AE based on the clinical judgment of the Investigator.

